1.0 BACKGROUND

The purpose of this study is to test whether administration of levetiracetam (LEV), a commonly used anti-epileptic that alters neurotransmitter release, can reduce hippocampal hyperactivity. Specifically, we will utilize two functional magnetic resonance imaging (MRI) techniques: 1) blood oxygen level dependence (BOLD) contrast will assess activity with a visual scene processing task that engages the anterior hippocampus and 2) arterial spin labeling (ASL) will assess baseline activity. Previous studies in people with psychotic disorders have shown that the hippocampus is hyperactive and more activity correlates with worsening of clinical symptoms. Therefore, the aim of this study is to use an intervention to further understand the underlying mechanisms of the hippocampus in psychosis.

Background and Significance

The lifetime prevalence of schizophrenia is about 0.7% (Saha et al., 2005), and the burden of illness is significant not only for patients but also society at large (Lehman et al., 2004). One contribution to this massive disease burden is the lack of optimal treatments, as only 20% of diagnosed individuals reach favorable treatment outcomes (Association, 2016). An important factor in the lack of treatment development for psychotic disorders is the unavailability of predictors that can be used to determine if therapeutic candidates elicit their targeted biological effects (Tregellas, 2014).

A growing body of literature demonstrates that the anterior hippocampus is hyperactive in patients with schizophrenia (Schobel et al., 2009; Talati et al., 2014) and clinical high risk patients that progress to developing schizophrenia (Modinos et al., 2018; Schobel et al., 2013). This hyperactivity is the result of an excitation-inhibition imbalance in the hippocampus (Heckers and Konradi, 2015; Uhlhaas, 2013). Excitatory, glutamatergic pyramidal cells comprise 90% of hippocampus neurons (Olbrich and Braak, 1985). The remaining neurons are inhibitory, GABAergic interneurons that modulate and synchronize overall activity to exert ultimate hippocampus activity (Freund, 2003; Klausberger and Somogyi, 2008). Different models have attributed the hippocampal excitation-inhibition imbalance to alterations in neurotransmitters glutamate or GABA (Benes, 1999; Stan et al., 2015) or interneuron abnormalities (Heckers and Konradi, 2015; Lodge et al., 2009).

This human laboratory study seeks to use an intervention to further understand the underlying mechanisms of the hippocampus in psychosis. This will be accomplished by using LEV. While the exact mechanism of action of LEV continues to be evaluated, evidence shows that it regulates neuronal synaptic exocytosis and calcium-induced neurotransmitter release (Lynch et al., 2004). Therefore, LEV may have a therapeutic effect on excitation-inhibition imbalance of the hippocampus. LEV has an overwhelming amount of evidence for modulating neuronal activity and has been established as a FDA-approved anti-epileptic drug for almost two decades (Lyseng-Williamson, 2011). Most other anti-epileptic medications affect ion channels, which are functionally "upstream" from synaptic exocytosis. Because of this, LEV has a more favorable side-effect profile when compared to other FDA-approved anti-epileptic drugs. Additionally, LEV has a lower risk of pharmacokinetic interactions with antipsychotics, and a lower risk of cognitive side effects when compared to other anti-epileptic drugs (Patsalos, 2000).

Neuroimaging studies provide the best opportunity to test the hypothesis of an excitation-inhibition imbalance in the hippocampus (Logothetis, 2008). Our lab has recently developed a functional MRI task that allows for robust, individual-subject level analysis of the hippocampus (McHugo et al., 2019). Based on the evidence provided above, LEV is an ideal intervention to assess hippocampal activity. Because hippocampal activity correlates to clinical symptoms (Friston et al., 1992; Gur et al., 1995; Liddle et al., 1992), can predict clinical progression, has translational capabilities (Gozzi et al., 2010, 2008; Stevens and Wear, 1997), and has recently been shown to function as a therapeutic target for schizophrenia (Bakker et al., 2012; Gill and Grace,

2014; Gomes et al., 2016; Koh et al., 2018; Perez and Lodge, 2014; Smucny and Tregellas, 2017), it is an ideal neural mechanism to study.

2.0 RATIONALE AND SPECIFIC AIMS

Our central hypothesis is that in psychotic disorders, LEV will safely normalize hippocampal hyperactivity. This will result in an increase in recruitment and activity of the hippocampus during tasks that specifically engage the hippocampus. In this project, we will test our hypothesis in 40 psychotic patients and 40 healthy control subjects. Following baseline clinical assessments, participants will undergo a 2-way crossover, double-blind, randomized controlled study with low-dose LEV and placebo. We will use neuroimaging methods to test the effect of the intervention.

Study Aim: To determine whether administration of low-dose, oral LEV modulates hippocampal hyperactivity

Hypothesis 1: Oral LEV will decrease, in a dose-response relationship, hippocampal activity in healthy control subjects and psychotic patients (ASL study).

Hypothesis 2: Oral LEV will normalize hippocampal recruitment in patients (Scene-processing fMRI study).

Hypothesis 3: Compared with healthy control subjects, psychotic patients will show higher hippocampal activity (ASL study) and reduced hippocampal recruitment (Scene-processing fMRI study).

3.0 ANIMAL STUDIES AND PREVIOUS HUMAN STUDIES

3.1 Animal Studies: Animal models have been used to study the relationship between hippocampal activity and variety of different diseases and conditions. Treatment with LEV has been found to improve memory in both aging (Devi and Ohno, 2013; Koh et al., 2010; Suberbielle et al., 2013) and Alzheimer's disease (Devi and Ohno, 2013; Hall et al., 2015; Sanchez et al., 2012; Suberbielle et al., 2013) animal models that are associated with increased neural activity in the hippocampus.

Importantly, all of these studies used doses substantially lower than those used in seizure models. Koh et al. (2010) demonstrated improvements in spatial memory task performance at both 5 and 10 mg/kg. Typical antiepileptic doses of LEV in rodent seizure models are in a range of 50-150 mg/kg. Devi and Ohno (2013) used 10-20 mg/kg to improve memory in a contextual fear conditioning paradigm. Hall et al. (2015) used a dose of 75 mg/kg/day to reverse ion channel depletion associated with hippocampal dendritic hyperexcitability and to reverse abnormalities in a spatial memory behavioral task. Suberbielle et al. (2013) also used 75 mg/kg/day to demonstrate improvements in learning and memory. Sanchez et al. (2012) reported that LEV loses both its antiepileptic effect and its beneficial effect on behavioral and molecular abnormalities in mice when given at high doses. Only low doses of LEV reversed learning and memory abnormalities and abnormal alterations in the expression of synaptic activity. Importantly, of seven FDA-approved anti-epileptics tested with differing methods of action, only LEV had this effect (Sanchez et al., 2012).

Treatment with LEV in animal models of schizophrenia has also demonstrated improvements in cognitive symptoms. The inability to filter brain responses to repetitive stimuli, as evidenced by poor inhibition of early (50 ms post-stimulus) evoked brain response to the second of two closely paired, identical auditory click stimuli is a feature of schizophrenia (Potter et al., 2006). This is measured in preclinical models using *in vivo* recordings of auditory-evoked potentials from the mouse hippocampus. Drugs that improve gating in rodents have demonstrated similar effects in human patients, supporting the utility of this gating model as a translational tool (Olincy and Stevens, 2007). A 10 mg/kg dose of LEV was found to improve auditory gating in a mouse model of schizophrenia (Smucny et al., 2015).

Wandschneider et al. (2014) studied a population of patients with temporal lobe epilepsy (TLE). This population has previously been shown to be unable to deactivate their diseased hippocampi with increasing cognitive demands (Stretton et al., 2012). In a retrospective study design, about 55% of TLE patients received varying doses of LEV (median (interquartile range) = 2,500 mg/day (1,000)) in addition to other anti-epileptic drugs. Patients on LEV showed normalization of functional network deactivations in the right temporal lobe in right TLE during a right-lateralizing visual-spatial task, and in the left temporal lobe during a verbal task. Post-hoc analysis showed that both hippocampi were more abnormally activated in patients with lower doses. These findings suggest that LEV is associated with restoration of normal activation patterns in the hippocampus.

Two additional studies have used LEV as an intervention in a fMRI study in epilepsy patients (Zhang et al., 2018, 2017). Although they did not employ cognitive tasks in the fMRI study, we highlight them here to demonstrate that fMRI is sufficient tool to detect group level changes with an intervention of LEV.

4.0 INCLUSION/EXCLUSION CRITERIA

Inclusion criteria for psychosis subjects

1. Men and women age 18 - 65.
2. Communicative in English.
3. Provide voluntary, written informed consent.
4. Physically healthy by medical history.
5. BMI > 17.5 and < 45.
6. Diagnosis of a psychotic disorder confirmed by Structured Clinical Interview for DSM-V (SCID) or diagnostic interview with a trained clinician.
7. Stable medication regimen over at least the past two weeks, including the use of either an oral or intramuscular administration of an antipsychotic medication.

8. For females, no longer of child-bearing potential, or agreeing to practice effective contraception during the study (e.g., established use of oral, injected or implanted hormonal methods of contraception; placement of an intrauterine device [IUD] or intrauterine system [IUS]; barrier methods: condom with spermicidal foam/gel/film/cream/suppository or occlusive cap [diaphragm or cervical/vault caps] with spermicidal foam/gel/film/cream/suppository; male partner sterilization; or true abstinence when this is in line with the preferred and usual lifestyle of the subject); and,
9. For females of child-bearing potential, must have a negative urine pregnancy test before MRI and drug administration.
10. Not breastfeeding/nursing at time of screening or at any time during the study.

Exclusion criteria for psychosis subjects

1. Age less than 18 or greater than 65.
2. Not communicative in English.
3. Unable to provide written informed consent.
4. Current medical or neurological illness.
5. History of severe head trauma.
6. BMI < 17.5 or > 45.
7. Meets criteria for diagnosis of substance or alcohol use disorder within the past month.
8. Positive urine pregnancy test during the study.
9. Breastfeeding/nursing at time of screening or at any time during the study.
10. Conditions that preclude MR scanning (as defined in the Screening Form)
11. Conditions that preclude study drug administration (as defined in the Screening Form)

Inclusion criteria for healthy controls

All of the above except for subjects will be psychiatrically healthy and not taking psychotropic or potentially psychoactive prescription medication.

Exclusion criteria for healthy controls

All of the above and in addition:

1. Current use of psychotropic or potentially psychoactive prescription medication.
2. Major psychiatric disorder as determined by DSM-V (major depression, bipolar disorder, obsessive compulsive disorder, post-traumatic stress disorder, etc)

5.0 ENROLLMENT

5.1. Recruitment: Study participants will be recruited from the **Psychiatric Genotype/Phenotype Repository (PGPR, IRB #080606)**: The PGPR study includes a clinical interview during which diagnostic and clinical history data is collected. At the end of this interview, individuals will be asked by one of the key research personnel listed on this application if they are interested in participating in the study. The PI of this study is the same PI for the PGPR study. Subjects will be read a script describing the study. Subjects will be told that the study is separate from their participation in the PGPR study and choosing not to participate in the study will not affect their participation in the PGPR study. In addition, individuals that have previously completed the PGPR study may be contacted and asked if they would like to participate in the study. The consent form for the PGPR study states that subjects may be contacted and asked if they would like to take part in future studies, if they agree. Subjects will be read a script telling them about the study. The telephone screening form used for the Psychiatric Genotype/Phenotype study will be re-administered to make sure that they still meet the original criteria for participating in the Psychiatric Genotype/Phenotype Study (i.e. age, physical health, and MRI requirements).

We will make every effort to recruit equal numbers of men and women. We will not exclude subjects based on gender or minority status. We minimize coercion throughout the study by repeatedly informing subjects that

they may discontinue study procedures at any point, or opt-out of any specific part of the study they become uncomfortable with completing.

We plan to recruit up to 80 subjects (up to 40 healthy control subjects and up to 40 patients with psychotic disorders) for the study. We hope to acquire analyzable data from at least 20 control subjects and 20 patients.

Subjects who were recently recruited in other psychiatry studies also conducted by this PI (e.g. genotype/phenotype studies) may not be required to participate in components of this study that would duplicate efforts (e.g. SCID interview). We plan to include data from those studies in the analyses of data from this study. Participants will be compensated for all activities they complete.

5.2 Monetary Compensation: All study subjects will be remunerated \$25 for completion of the screening and consent form, regardless of their decision to enroll in the study or their eligibility to enroll. Because of the study design, subjects only yield meaningful primary outcome data if they complete all visits. They will therefore be compensated an additional \$275 at the completion of the remaining study visits. This incentivization is designed to yield greater benefit from the research, thereby improving the risk/benefit ratio of the study.

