Survey). If the subject is unable to answer any of the questions, or if the subject demonstrates a lack of understanding, the investigator or research staff member will then review the details of the study again. Subjects who are unable to answer the questions, even after additional information is provided, will be excluded from the study.

3. The subject will be informed that regardless of whether or not they take part in this research study, it will not affect their treatment, payment or enrollment in any health plans or affect their ability to get benefits or care in any way.
4. The subject will be provided with copies of the signed consent form and the Informed Consent Survey (including the answers given) at the time of the initial visit.

It will be emphasized to all subjects that their participation is completely voluntary, and that even after signing the consent document they are still free to withdraw from the study at any time; in which case they will be compensated for the portion(s) of the protocol they did complete.

6.2 Diagnostic Assessment: Under the supervision of the PI, a trained research assistant will administer the Structured Clinical Interview for DSM-V (SCID) (First, 2015), a clinician-rated assessment of psychiatric disorder. Diagnostic assessments may be conducted electronically with zoom or in the research offices at the Psychiatric Neuroimaging Program. Diagnoses are made both for current and lifetime periods. The SCID is reliable and valid in psychiatric populations, with coefficients of agreement between .70 and 1.0 for depressive, anxiety, and substance use disorders (significantly superior to standard clinical interview). We will supplement the SCID with the psychotic disorders module from the Diagnostic Interview for Genetics Studies (DIGS), which provides more information for the accurate differential diagnosis of psychotic disorders. The Informed Consent Form will include check box indicating if the study participant is being asked to complete the Diagnostic Interview. The SCID can take from 30 minutes to several hours to complete.

If significant suicidal thought is noted during the evaluation, the patients will be encouraged to talk to their treatment providers. If the patient is judged to be at imminent risk of self- or other-harm, standard procedures will be followed (found in Procedures in Response to Suicidal Ideation document).

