10.0 STUDY WITHDRAWAL/DISCONTINUATION

Subjects will be withdrawn from the study for safety considerations, non-compliance with study procedures, difficulties with scheduling or participation, excess movement or anxiety during scanning, or other reasons that the PI or study coordinators conclude will impair the scientific utility of the study. Subjects will be provided an explanation by the investigator if they are withdrawn from the study. In addition, subjects can voluntarily withdraw from the study at any time.

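### Section 5.2 ties 275 of 300 dollars to completing every visit, in conflict with the promise in 6.1 to pay those who withdraw for what they did, and pay after withdrawal by the PI is not settled

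*Combined protocol and SAP*

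**What the plan says.** Section 5.2 (Monetary Compensation) sets two payments. The first, in dollars, is "25 for completion of the screening and consent form, regardless of their decision to enroll in the study or their eligibility to enroll". The second is "275 at the completion of the remaining study visits". The reason given for the second is that "subjects only yield meaningful primary outcome data if they complete all visits", and the section adds: "This incentivization is designed to yield greater benefit from the research". It gives no amount for attending Visit 2 without Visit 3.

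Section 6.1 (Screening and Consent) deals with people who decide to leave after signing, "in which case they will be compensated for the portion(s) of the protocol they did complete". Staff are to emphasize this to every participant.

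Section 5.1 (Recruitment) closes its paragraph on components already done in the investigator's other studies with a general statement: "Participants will be compensated for all activities they complete". The same section describes how coercion is kept low, by repeatedly telling participants that "they may discontinue study procedures at any point, or opt-out of any specific part of the study".

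Section 10 lists grounds on which the study team may end participation, beginning: "Subjects will be withdrawn from the study for safety considerations". It says nothing about payment.

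**The concern.** Visits 2 and 3 are the two dosing and scanning visits of the crossover. A participant who leaves between them has taken a blinded capsule dose, given blood and been scanned once. Section 5.2 attaches no money to that visit by itself, whereas 6.1 says the completed part is paid. Staff answering a participant who asks what happens on stopping now would find different answers in the two sections.

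Two things are at stake. The first is consistency between what participants are told and what they are paid, in a study that enrols people with psychotic disorders and says it seeks to minimize coercion. The second is the pressure that an all-or-nothing sum creates at one particular moment, after the first dosing visit and before the second. Someone who felt unwell after Visit 2 would have a financial reason to return anyway, and might hesitate to mention a reaction that could lead the PI to end their participation.

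**Working it through.** The check is a side-by-side reading plus simple arithmetic. No power, sample-size or error-rate figure is involved.

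**Inputs**
- Screening and consent payment: 25 dollars (5.2).
- Payment for the remaining visits: 275 dollars, one sum (5.2).
- Visits: three in all, with dosing and MRI at Visits 2 and 3 (6.0, 6.4, 6.5).

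**Shares**
- Total = 25 + 275 = 300 dollars. The protocol does not print this total; it is the sum of the two stated amounts.
- Share tied to completion = 275/300 = 0.917, or 91.7%.
- Share guaranteed = 25/300 = 0.083, or 8.3%.

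**One participant under each rule: completes Visits 1 and 2, not Visit 3**

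| How participation ends | 5.2 | 6.1 | 5.1 | Section 10 |
|---|---|---|---|---|
| Participant withdraws | 25 dollars | Completed parts are paid; no rate given | Completed activities are paid; no rate given and withdrawal not mentioned | Silent on pay |
| PI withdraws the participant | 25 dollars | Not covered | As above | Silent on pay |

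**Size of the gap.** Under 6.1 the voluntary withdrawer is owed more than 25 dollars and, having missed a visit, presumably less than 300. The documents do not fix the point within that range. As an illustration only, assume the 275 dollars were divided equally between Visits 2 and 3: 275/2 = 137.50, so the participant would receive 25 + 137.50 = 162.50 dollars, against 25 under 5.2.

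**Is 5.2 only a statement of when payment is made?** The section argues from the need for complete data to the 275-dollar payment, and then calls the arrangement an incentive. A sum that is owed whether or not the visits are completed would give no such incentive. The natural reading is therefore a condition on payment.

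**The case against.** The strongest reply is that 5.2 never says the 275 dollars is forfeited on early stopping. It states what completers receive and 6.1 states what withdrawers receive, so a site could honour both, and all that is missing is a part-payment figure. This has some force: there is no explicit forfeiture clause, and a reader who infers that compliance with both sections is strictly impossible goes too far. But the reply does not fit the reasoning in 5.2, which makes completion the ground for the payment. Even on the kindest reading, staff have no amount to pay.

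Four other cautions stand.

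- The promise in 6.1 concerns voluntary withdrawal. It should not be read as granting Visit 2 pay to someone withdrawn by the PI; for that case 6.1 leaves a gap and gives no contrary rule.
- The sentence in 5.1 is general and does not mention withdrawal. Neither 5.1 nor 6.1 sets a rate, so neither promises pro-rated pay.
- A reader might infer that the scheme rewards hiding a reaction and biases adverse-event counts downward. The documents do not support this as a finding. Section 9 defines, grades and reviews adverse events but does not say how they are elicited. Nothing says that reporting an event leads to withdrawal or costs money; failing to complete does. Section 11 plans no adverse-event analysis, and no figure sizes such an effect. If staff give the assurance in 6.1 as written, the pressure is also reduced.
- The consent form is not among the documents available, so a per-visit schedule there cannot be ruled out.

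A completion incentive also has a legitimate purpose in a two-period crossover, and its size is for the sponsor and the IRB to judge.

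**Conclusion.** The conflict between 5.2 and 6.1 is real for a participant who voluntarily stops after Visit 2, and 5.2 sits poorly with the general payment statement and the anti-coercion aim in 5.1. It concerns 275 of 300 dollars, or 91.7% of the total. For withdrawal by the PI, including for safety, 6.1 and section 10 are silent, so 5.2 taken alone leaves that participant with 25 dollars, or 8.3%.

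This rests on reading 5.2 as a condition, which its own rationale supports, and on the protocol text alone, without the consent form. The possible effect on stopping, or on reporting a reaction, after the first dosing visit is a reasonable inference about incentives and should be stated as no more than that. The point does not threaten the validity of the imaging comparison, but it should be corrected because it affects what participants are told and paid.

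**What to change.** Amend 5.2 so that it agrees with 5.1 and 6.1:

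1. Replace the single 275 dollars with a stated amount for each of Visits 2 and 3. If a completion supplement is kept, make it the smaller part, at a level for the sponsor and IRB to set.
2. State that visits attended are paid whether the participant withdraws or is withdrawn by the PI, including because of an adverse event, and cross-refer to this from section 10.
3. Check that the consent form carries the same wording.

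The cost is a short amendment, part-payments to those who stop early, and a slightly weaker incentive to return for Visit 3. If the stated amounts, with any supplement, still add up to 275 dollars, no participant would receive more than the 300 dollars that 5.2 already gives a completer. Nothing in the dosing, endpoints or analysis needs to change.
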